### **Procedures for discontinuation of a subject from investigational product**

A subject that discontinues treatment will always be asked about the reason(s) for discontinuation and the presence of any AEs. The Principal Investigator/sub-investigator will perform the best possible observation(s), test(s) and evaluation(s) as well as give appropriate medication and all possible measures for the safety of the subject. They will also immediately inform AstraZeneca of the withdrawal.

If a subject is withdrawn from study, see Section 3.7

### **3.7 Criteria for withdrawal from study**

#### **3.7.1 Screen failures**

Screening failures are subjects who do not fulfil the eligibility criteria for the study, and therefore must not be initiated on study treatment. These subjects should have the reason for study withdrawal recorded as 'Screen failure' (the potential subject who does not meet one or more criteria required for participation in a trial).

### 3.7.2 Withdrawal of the informed consent

Subjects are free to withdraw from the study at any time (investigational product and further assessments), without prejudice to further treatment.

A subject who withdraws consent will always be asked about the reason(s) and the presence of any adverse events (AE). AEs will be followed up (See Section 6.4); subject diaries, glucometer and study drug should be returned by the subject.

If a subject withdraws from participation in the study, then his/her enrolment code cannot be reused. Withdrawn subjects will not be replaced.

### 3.8 Discontinuation of the study

The study may be stopped if, in the judgment of AstraZeneca, trial subjects are placed at undue risk because of clinically significant findings that meet individual stopping criteria or are otherwise considered significant

Regardless of the reason for termination, all data available for the subject at the time of discontinuation of follow-up must be recorded in the CRF. All reasons for discontinuation of treatment must be documented.

In terminating the study, the Sponsor will ensure that adequate consideration is given to the protection of the subjects' interests.

## 4 STUDY PLAN AND TIMING OF PROCEDURES

This is a 24-week open label prospective study. After eligibility check as per criteria mentioned in section 3.1 and 3.2 patients, will be recruited in the study and procedures as mentioned in below table will be performed at various scheduled visits.

Table 1

Assessments	Visit 1	Visit 2	Visit 3 #	Visit 4 #	Visit 5	Visit 6 #	Visit 7	Visit 8 #	Visit 9 (EOT)	Visit 10 (EoS)
	Enrolment* (-1 wk)	(0 Wk)	(1 Wk)	(4 wk)	(8 wk)	(12 wk)	(16 wk)	(20 wk)	(24 wk)	(26 wk)
Window period (Days)	(±5)	(±5)	(±2)	(±2)	(±5)	(±2)	(±5)	(±2)	(+5)	(+2)
Informed Consent	X									
Physical Exam	X	X			X		X		X	X

Vital Signs	X	X			X		X		X	X
Eligibility check	X	X								
HbA1c	X	X			X		X		X	X
Fasting Plasma Glucose (FPG)**		X			X		X		X	X
Weight & Height		X			X		X		X	X
Waist circumference		X			X		X		X	X
BMI (Body Mass Index)		X			X		X		X	X
Blood Pressure		X			X		X		X	X
Safety labs	X	X			X		X		X	X
ECG		X					X		X	X
AE assessment		X	X	X	X	X	X	X	X	X
Urinalysis	X	X			X		X		X	X
UPT (WOCBP)	X	X			X		X		X	X
IP dispensation		X			X					
IP accountability		X	X	X	X	X	X		X	X

\*enrolment and Visit 2 can coincide to enter patient into the study, #telephonic visit

\*\* Subjects must be in a fasting state at least 8 hours prior to study visit.

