### **3.6 Discontinuation of investigational product**

Every attempt will be made to retain subject on study medication. Subjects who discontinue study medication during the treatment period will be performed the End of treatment visit (Visit no: 9) and will be contacted for 2 weeks later and asked for the presence of any AEs.

Subjects are free to discontinue investigational product at any time, without prejudice to further treatment and follow up.

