## **6.3 Recording of adverse events**

### **6.3.1 Time period for collection of adverse events**

Adverse Events will be collected throughout the treatment period and including the follow-up period of one week after end of study. SAEs will be recorded from the time of informed consent.

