### **6.3.2 Follow-up of unresolved adverse events**

Any AEs that are unresolved at EOS visit are followed up by the Investigator for as long as medically indicated, but without further recording in the CRF. AstraZeneca retains the right to request additional information for any subject with ongoing AE(s)/SAE(s) at the end of the study, if judged necessary.

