## 8 STATISTICAL ANALYSES BY ASTRAZENECA

This is an India regulatory requirement study. Objective is to establish that FDC of Dapagliflozin 10mg / Saxagliptin 5 mg is a safe treatment option in Indian T2DM patients. This study is planned as prospective study on 200 patients in single arm open label study. CCI

Data will be summarized using descriptive statistics. Continuous variables will be summarized using the number of observations, mean, SD, median, and range as appropriate. Categorical values will be summarized using the number of observations and percentages as appropriate.

The safety analysis population will include all patients who sign the ICF and receive at least one dose of study medication.

The safety analysis population is also applicable to the efficacy analysis, and any efficacy measurements collected before the study medication discontinuation will be included. Last on treatment observation will be carried forward to impute the missing data at week 24.

Any AE occurring within 2 weeks of discontinuation of investigational product (ie, the last dose of study medication) will be included in the AE summaries. Any events in this period that occur after a patient has received further therapy for (following discontinuation of study drug) will be flagged in the data listings. Adverse event rates shall be stratified by age/gender/baseline medications. Annualised event rate shall also be presented in addition to the incidence rate during the study. Mean change in HbA1C from baseline to 6 months for patients will be analysed using paired t test / Wilcoxon signed-rank test at 5% level of significance.

The study is designed in accordance with the Health Authority requirements in India. It is intended to provide information regarding the safety profile for patients in India, and will contribute additional information to the overall safety profile of Dapa-Saxa FDC. Due to the small sample size, this study should not be directly compared to the data from any other country.

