### **9.3 Study timetable and end of study**

The end of the study is defined as ‘the last visit of the last subject undergoing the study’.

The study may be terminated at individual centres if the study procedures are not being performed according to GCP, or if recruitment is slow. AstraZeneca may also terminate the entire study prematurely if concerns for safety arise within this study or in any other study with Dapagliflozin / saxagliptin fixed dose combination.

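### Visit 10 is timed in study weeks rather than from the last dose, so a late Visit 9 can put the last scheduled AE check up to 5 days before section 8's 2-week window closes (minor)

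*Protocol*

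**What the plan says.** **Visit timing.** The Table 1 header (section 4) places Visits 8, 9 and 10 at "20 wk) (24 wk) (26 wk". The row headed "Window period (Days" gives +5 for Visit 9 (EOT) and +2 for Visit 10 (EoS). No footnote links Visit 10 to the actual date of Visit 9 or to the last dose. AE assessment is marked at both visits, and nothing is scheduled after Visit 10.

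**Counting rule.** Section 8 states: "Any AE occurring within 2 weeks of discontinuation of investigational product (ie, the last dose of study medication) will be included in the AE summaries".

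**Early stoppers.** Under section 3.6, subjects who stop during the treatment period have the end-of-treatment visit and then "will be contacted for 2 weeks later and asked for the presence of any AEs".

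**End of AE collection.** Section 6.3.1 states: "Adverse Events will be collected throughout the treatment period and including the follow-up period of one week after end of study". Section 6.3.2, referring to the case report form, states: "Any AEs that are unresolved at EOS visit are followed up by the Investigator for as long as medically indicated, but without further recording in" it. Section 9.3 states: "The end of the study is defined as ‘the last visit of the last subject undergoing the study".

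**The concern.** The primary objective is to describe the AE profile, and section 8 defines which post-treatment events enter that description by time since the last dose. The nominal schedule fits, since week 24 to week 26 is 2 weeks. The windows do not preserve the fit. Visit 9 can move later while Visit 10 stays near week 26, so every day of delay at Visit 9 comes out of the follow-up. A site that complies fully can hold a completer's last AE assessment before the counting window has closed. Events in the remaining days would then reach the database only if the subject volunteered them.

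**Working it through.** **Inputs.** Visit 9 is at week 24, +0 to +5 days; Visit 10 is at week 26, +0 to +2 days (both Table 1). The AE counting window is 14 days after the last dose (section 8).

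**Nominal schedule.** 24 × 7 = 168 and 26 × 7 = 182, so the planned gap is 182 − 168 = 14 days. This agrees with section 8.

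**With the windows.** Visit 9 falls on days 168 to 173 and Visit 10 on days 182 to 184. Both are counted from Visit 2, so the ±5-day window at Visit 2 cancels.

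- Shortest gap: 182 − 173 = 9 days.
- Longest gap: 184 − 168 = 16 days.
- In general, with Visit 9 delayed by d days, the gap runs from 14 − d to 16 − d.

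| Visit 9 delay (days) | Possible gap to Visit 10 (days) | Can 14 be reached? |
|---|---|---|
| 0 | 14 to 16 | always |
| 1 | 13 to 15 | only if Visit 10 is at least 1 day late |
| 2 | 12 to 14 | only if Visit 10 is 2 days late |
| 3 | 11 to 13 | no |
| 4 | 10 to 12 | no |
| 5 | 9 to 11 | no |

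Of the 6 × 3 = 18 permitted date pairs, 1 + 2 + 3 + 3 + 3 = 12 give less than 14 days. That counts calendar combinations. It is not a probability and not a share of patients.

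**From visit gap to off-drug time.** This step depends on when the last dose is taken.

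- If dosing continues to Visit 9, the off-drug interval is the gap above, and the largest shortfall is 14 − 9 = 5 days (5/14 = 36% of the window, in the worst case for one subject).
- If dosing stops at day 168 whatever the date of Visit 9, the interval from last dose to Visit 10 is 182 − 168 = 14 to 184 − 168 = 16 days, and there is no shortfall.

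**Effect of section 6.3.1.** If its extra week runs from each subject's own Visit 10, the shortest collection period after a last dose at Visit 9 is 9 + 7 = 16 days, which exceeds 14.

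**Check of the fix.** With Visit 10 at 14 (+2) days after the last dose, the interval is 14 to 16 days in every case. For a last dose on day 173, Visit 10 moves from days 182–184 to days 187–189, a shift of 5 days.

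**The case against.** The strongest reply is that section 8's clock starts at the last dose, not at Visit 9. The protocol plans 24 weeks of treatment and nowhere says that tablets continue to a late Visit 9. A reader might infer from Table 1 that completers are followed for only 9 days off drug. The document supports that only on the assumption of dosing to Visit 9, so the point must be stated conditionally. The assumption is nevertheless plausible: Visit 9 is labelled end of treatment, and section 8 admits only efficacy data collected before study drug is discontinued, which would exclude a late Visit 9 if dosing had already ended at day 168.

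The second reply is section 6.3.1. Read per subject, its extra week covers the whole window, and section 6.3.5 collects spontaneously reported events without needing a visit. Section 6.3.2 ends CRF recording only for events already unresolved at the end-of-study visit; it does not bar new ones. So it would be too strong to say that late events are necessarily lost. What survives is that no contact is scheduled in that week to elicit events, and that section 9.3 defines end of study for the trial as a whole, so the start of the extra week for an individual subject is unclear.

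Three further inferences should not be drawn:

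- **Section 3.6 is not undermined.** The contact for early stoppers is already timed relative to stopping, so the week 26 column does not shorten it.
- **Nothing says that Visit 10 laboratory, ECG and vital-sign values are pooled as a single time point.** How they are summarised may be set in an analysis plan that is not shown.
- **The efficacy outcomes are not affected by the Visit 10 date.** They are defined at week 24 from on-treatment measurements.

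**Conclusion.** The point holds in a limited form. The Visit 9 and Visit 10 windows allow a gap of 9 to 16 days, and with Visit 9 at +3 to +5 no permitted Visit 10 date reaches 14 days. On the assumption that dosing runs to Visit 9, the schedule does not guarantee a planned AE assessment at or after the close of section 8's own counting window. Section 6.3.1 may cover the gap in principle but has no scheduled contact behind it and uses an end point that section 9.3 defines at trial level.

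The effect is small. It is confined to completers with a late Visit 9, and for them to events in at most the last 5 days of the window. Five days set against the roughly 182 days from Visit 2 to Visit 10 is 5/182, or under 3% of one subject's observation. How many completers would attend late is not known from the protocol. Severity: minor.

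**What to change.** 1. In Table 1, replace the week 26 (+2) timing of Visit 10 with 14 days after the last dose (+2 days). This uses the 2 weeks that section 8 already states and gives 14 to 16 days of scheduled follow-up for every completer, whichever way the dosing question is answered.
2. State in the protocol how the last dose relates to the date of Visit 9, so that the anchor is unambiguous. This note takes no view on which arrangement is right.
3. Reconcile section 6.3.1 with the new timing: define the end of AE collection per subject, from the same anchor, and make it consistent with sections 6.3.2, 8 and 9.3. If the extra week is kept, schedule a contact at its end.

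Section 3.6 needs no change for this point.

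The cost is a Table 1 header change and a short clarification of wording. Some last visits move by up to 5 days.

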#### **4.1 Screening/Enrolment period**

*Procedures will be performed according to the Study Plan.*

Eligible patients will be enrolled into the study and unique identification number will be provided to each patient.

#### **4.2 Treatment period**

*Descriptions of the procedures for this period are included in the Study Plan.*

#### **4.3 Follow-up period**

*Descriptions of the procedures for this period are included in the Study Plan.*

### **5 STUDY ASSESSMENTS**

*Electronic Case Report Forms (eCRF) will be used for data collection and query handling. The investigator will ensure that data are recorded on the eCRF as specified in the Clinical Study Protocol and in accordance with the instructions provided.*

The investigator ensures the accuracy, completeness, *eCRFs include:* timeliness of the data recorded and of the provision of answers to data queries according to the Clinical Study Agreement. The investigator will sign the completed electronic Case Report Forms. A copy of the completed electronic Case Report Forms will be archived at the study site.

#### **5.1 Efficacy assessments**

##### **5.1.1 Glycosylated Haemoglobin -HbA1c**

HbA1c is a well-established measure of glycemic efficacy and considered to be an acceptable secondary endpoint the assessment for the determination of glycemic efficacy. HbA1c will be analysed by a central laboratory according to the procedures described in the Laboratory Manual which will be distributed to each study site during site initiation.

##### **5.1.2 Fasting Plasma Glucose (FPG)**

FPG is a well-established measure of glycemic efficacy and considered to be an acceptable secondary endpoint.

##### **5.1.3 Weight and height**

The subject's weight will be recorded in kilogram (kg) to one decimal place, on a fasting stomach with light clothing and no shoes. The subject's height will be recorded in centimetres, with no shoes. All readings should be recorded as accurately as possible and the same scale should be used for all assessments for a given subject.

## 5.2 Safety assessments

The Principal Investigator is responsible for ensuring that all staff involved in the study is familiar with the content of this section.

### 5.2.1 Laboratory safety assessments

Blood samples shall be collected and processed as per the local affiliated laboratory criteria.

Deterioration as compared to baseline in protocol-mandated laboratory values, vital signs and other safety variables will only be reported as AEs if they are clinically significant, fulfil any of the SAE criteria or are the reason for discontinuation of treatment with the investigational product, or require the subject to receive specific corrective therapy. If a deterioration in a laboratory value/vital sign is associated with clinical signs and symptoms, the sign/symptom will be reported as an AE and the associated laboratory result/vital sign will be considered as additional information. Any new or aggravated clinically relevant abnormal medical finding at a physical examination or ECG evaluation as compared with the baseline assessment will be reported as an AE.

Clinically relevant deterioration in non-protocol-mandated measurements will be reported as AE(s).

Wherever possible the reporting investigator uses the clinical, rather than the laboratory term (eg, anaemia versus low haemoglobin value).

The following laboratory variables will be measured:

**Table 2 Laboratory Safety Variables**

Haematology/Haemostasis (whole blood)	Clinical Chemistry (serum or plasma)
B- Hematocrit	S/P-Creatinine
B-Leukocyte count	S/P-Bilirubin, total
B-Leukocyte differential count (absolute count)	S/P-Alkaline phosphatase (ALP)
B-Platelet count	S/P-Aspartate transaminase (AST)
B - Haemoglobin (Hb)	S/P-Alanine transaminase (ALT)
Urinalysis (dipstick)	S/P-Albumin
U-Hb/Erythrocytes/Blood	S/P-Potassium
U-Protein/Albumin	S/P-Calcium, total
U-Glucose	S/P-Sodium
	S/P-Creatine kinase (CK)

*The Investigator should make an assessment of the available results with regard to clinically relevant abnormalities. The laboratory results should be signed and dated and retained at centre as source data for laboratory variables. For information on how AEs based on laboratory tests should be recorded and reported, see Section 6.3*

**NB.** In case a subject shows an AST **or** ALT  $\geq 3 \times \text{ULN}$  **or** total bilirubin  $\geq 2 \times \text{ULN}$  please refer to Appendix B ‘Actions required in cases of combined increase of Aminotransferase and Total Bilirubin – Hy’s Law’, for further instructions.

### **5.2.2 Physical examination**

A brief physical examination should include the cardiovascular system, lungs, abdomen, and extremities, and any organ system pertinent to the subject’s signs, symptoms, or AEs. The subject should always be evaluated for the presence of oedema.

### **5.2.3 ECG**

#### **Resting 12-lead ECG**

A 12-lead ECG will be taken after the subject has been lying down resting. The ECG will be evaluated by the investigator and entered as ‘Normal’ or ‘Abnormal’ in the eCRF. If the ECG is evaluated as “Abnormal” the investigator should document the specific abnormality.

### **5.2.4 Vital signs**

Vital signs will be measured and recorded during each on site visit through the study duration.

#### **5.2.4.1 Pulse and blood pressure**

Pulse and BP readings should be taken while the subject is in a comfortable seated position with the arm supported at the level of the heart. All readings should be recorded. A standard mercury sphygmomanometer with a standardised cuff adapted to the size of the subject’s arm is recommended.

## **5.3 Other assessments**

Self-monitored blood glucose readings and hypoglycemic events will be collected in a subject diary and reviewed by the investigator at each visit.

### **5.3.1 Hypoglycemic events**

Subject self-monitoring of FBG is performed in order to reduce the risks associated with prolonged hyperglycemia and to confirm symptoms of hypoglycemia. Subjects will be asked to perform self-monitoring of FBG using glucometers provided by AstraZeneca. The subjects will receive instructions for the use of the glucometer according to the manufacturer’s instructions.

FBG should be self-monitored once every week between Visit 2 and 10. The results should be recorded in the subject diary, which will be collected and reviewed by the study personnel at each visit starting with Visit 3; record will be stored in the investigator study file.

The memory of the glucometer should be reviewed and compared with the readings in the subject's diary. The glucose values should be reviewed by the study personnel to identify any unusually high or low values, and to confirm that self-monitoring was performed by the subject. If fingerstick glucose values are discordant with central laboratory results or with clinical symptoms, the subject's glucometer should be tested and the glucometer instructions should be re-reviewed with the subject.

If self-monitored FBG is above 240 mg/dL then subject should repeat the FBG on the same day. If the second FBG value is above 240 mg/dL, the subject should contact the study centre and be scheduled for a central laboratory FBG measurement within one week.

If central laboratory values show similar values, the subject should be discontinued (if there is no obvious explanation, i.e. infections) and treated according to local practice.

A separate section in the eCRF will be used to document all reported episodes of hypoglycaemia. The subjects will be asked to check their blood glucose if they develop symptoms suggestive of hypoglycemia and to record specific symptoms in the subject diary. The Investigator is responsible for questioning the subject about all symptoms reported in the diary and for determining if they meet the clinical definition of hypoglycemia. Only symptoms and/or blood glucose values that meet the definition of hypoglycemia should be reported on the hypoglycemia eCRF pages.

A hypoglycemic event can be either:

- Symptoms of hypoglycemia with a low blood glucose reading (<63 mg/dL)
- A low blood glucose reading (<63 mg/dL [ $<3.5$  mmol/L])
- Symptoms of hypoglycemia without a blood glucose reading

Hypoglycemic episodes or discontinuation due to hypoglycemia should not be reported on the AE eCRF page unless the event fulfils protocol criteria for a SAE (see Section 6.4). In this case, an SAE must be reported in addition to the hypoglycemia eCRF pages for hypoglycemia.

Symptoms suggestive of hypoglycemia with an associated capillary or plasma glucose value  $\geq 63$  mg/dL ( $\geq 3.5$  mmol/L), should be recorded as an AE rather than as a hypoglycemic event. If the physician does not consider the glucose measurement to be accurate, however, the event should be documented as a hypoglycemic event in the hypoglycemia eCRF.

For the evaluation of hypoglycemic events, this study will use the definitions provided in the Committee for proprietary medicinal product (CPMP) guidance on clinical investigation of medicinal products in the treatment of diabetes mellitus, as described below.

- Major hypoglycemic events, defined as symptomatic events requiring external assistance due to severe impairment in consciousness or behaviour, with a capillary or plasma glucose value  $<54$  mg/dL ( $<3.0$  mmol/L) if available, and prompt recovery after glucose or glucagon administration.

- Minor hypoglycemic event, defined as either a symptomatic episode with a capillary or plasma glucose measurement <63 mg/dL (<3.5 mmol/L) regardless of need for external assistance or an asymptomatic capillary or plasma glucose measurement below 63 mg/dL (3.5 mmol/L), that does not qualify as a major episode
- Events suggestive of hypoglycemia, defined as a symptomatic event without a confirmatory blood glucose measurement.

Data to be collected for each hypoglycemic event:

- Date and time of episode (start and stop)
- Whether the subject was sleeping at the time of the event
- Whether symptoms were present, and list of symptoms
- Possible contributing factors
- Whether a fingerstick value was obtained, and if so, the plasma glucose value
- Whether intervention was needed for recovery
- How the episode was treated
- Whether recovery was prompt after treatment
- Time of last anti-diabetic agents administration
- Time of last meal and its contents

The subject diary will be reviewed and the hypoglycemic event data will be transcribed into the eCRFs at each clinical visit. A new diary for the next period will be handed over to the subject if needed. If a major hypoglycemic event or more than one minor event has occurred since the previous visit, the subject should contact the investigator.

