### **Drug name, dosage and mode of administration**

Patients will be given once daily fixed dose combination of Dapa/Saxa 10 mg/5 mg administered orally at the same time of the day throughout the study. Every attempt should be made to maintain patients on designated therapy for 24 weeks of study duration.

Other Medicinal products:

Patient will continue receiving medicines other than study drug as per investigators discretion. Patient may be eligible to receive additional glucose lowering drug if he meets rescue criteria as details provided in rescue therapy section. Sponsor will not provide any other medicine except investigational product Dapa/Saxa 10 mg/5 mg.

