### **3.1 Inclusion criteria**

For inclusion in the study subjects should fulfil the following criteria:

1. Provision of signed and dated, written informed consent prior to any study specific procedures according to local Indian procedure.
2. Male and female patients aged > 18 and above
3. Documented history of type 2 diabetes mellitus with HbA1c level >7.0% and ≤ 10% at screening visit
4. Patients who are on a stable dose of antidiabetic drugs (including on Metformin dose between 1000-2000mg) in the past 3 months
5. Female subjects must be 1 year post-menopausal, surgically sterile, or using an acceptable method of contraception (an acceptable method of contraception is defined as a barrier method in conjunction with a spermicide) for the duration of the study (from the time they sign consent) to prevent pregnancy. In addition, oral contraceptives, approved contraceptive implant, long-term injectable contraception, intrauterine device, or tubal ligation are allowed. Oral contraception alone is not acceptable; additional barrier methods in conjunction with spermicide must be used.

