## **7.7 Concomitant and other treatments**

Changes in concomitant medication should be avoided during study participation, with the exception of situations defined in this protocol, but medication, which is considered necessary for the subject's safety and well-being, may be given at the discretion of the investigators, who must decide if the subject should remain in study or need to be dismissed from study due to subject's safety or interference with study objectives.

The administration of all medication must be recorded in the appropriate sections of the electronic case report form (eCRF) with trade names, dosages, dates of starting and ending of medication and reason for therapy. If the patients glycemic status remains uncontrolled (HbA1c  $\geq 9\%$ , FBG  $\geq 240$  mg/dl (confirmed on readings taken on 2 consecutive days)

After having completed or discontinued the study, investigational product will be discontinued from sponsor but subjects will receive usual care and antidiabetic agents according to the investigator's judgement and according to local medical practice.

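### Section 5.3.1 discontinues a subject with confirmed fasting glucose above 240 mg/dL, while the synopsis and the prohibited-therapies list foresee rescue under criteria the protocol never completes

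*Protocol*

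**What the plan says.** **Section 5.3.1 (Hypoglycemic events).** The sequence is: "If self-monitored FBG is above 240 mg/dL then subject should repeat the FBG on the same day"; if the second reading is also above 240 mg/dL, the subject contacts the centre to "be scheduled for a central laboratory FBG measurement within one week"; then "If central laboratory values show similar values, the subject should be discontinued", unless something obvious such as an infection explains the reading. Treatment afterwards follows local practice.

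**Synopsis (Drug name, dosage and mode of administration).** An additional glucose-lowering drug is possible "if he meets rescue criteria as details provided in rescue therapy section". No threshold is given there. The same part asks that every attempt be made to keep patients on therapy for the 24 weeks.

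**Section 7.7, Prohibited Therapies.** Rescue therapies are exempt from the ban on other antidiabetic agents.

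**Section 7.7 (Concomitant and other treatments).** One sentence describes uncontrolled glycaemia as HbA1c of at least 9% and a fasting glucose of at least 240 mg/dL, "confirmed on readings taken on 2 consecutive days". It then stops without a main clause. The same section leaves it to the investigator whether a subject given necessary medication stays in the study, and it requires every medication in the eCRF with start date, stop date and reason.

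**Section 3.6 (General discontinuation criteria).** Nine items are listed. Hypoglycaemia, ketoacidosis, renal decline and pregnancy are named; hyperglycaemia is not.

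**Section 8.** Efficacy values count if taken before study-drug discontinuation, and the last on-treatment value is carried forward to week 24.

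**The concern.** An investigator with a persistently hyperglycaemic patient finds an instruction to discontinue in one place and permission to rescue in two others. The section that should decide between them is cited but absent. With about 8 centres, the choice may differ by site.

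The choice affects the data as well as the patient's care. Discontinuation ends on-treatment exposure, adds to the discontinuation count and freezes HbA1c and FPG at the last on-treatment value. Rescue with study drug continued does none of these, and lets the effect of the added drug into the week 24 value. The secondary efficacy results, the exposure behind the annualised event rates and the discontinuation count would then partly reflect which section a site happened to read.

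**Working it through.** The protocol states no figure on this point that could be reproduced. The check is a comparison of the passages, then simple arithmetic on what one reclassified subject changes.

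**Step 1. The passages side by side**

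| Element | Section 5.3.1 | Section 7.7, unfinished sentence | Synopsis and prohibited-therapies list |
|---|---|---|---|
| Measure | Fasting glucose | HbA1c and fasting glucose, with only a comma between them | None given |
| Level | Above 240 mg/dL | HbA1c at least 9%; glucose at least 240 mg/dL | None given |
| Confirmation | Same-day repeat, then central laboratory within one week | Readings on 2 consecutive days | None given |
| Time point | Weekly self-monitoring, Visits 2 to 10 | None given | During treatment |
| Action | Discontinue, unless explained | None stated | Added glucose-lowering drug permitted |

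**Step 2. Can one patient fall under both?** The two glucose levels differ only at exactly 240 mg/dL. A subject with sustained fasting glucose above that level can satisfy the confirmation rules of both 5.3.1 and 7.7. If the 7.7 sentence is the rescue criterion, that subject is due for discontinuation and eligible for rescue at once. If it is not, the protocol permits rescue under criteria stated nowhere in the document.

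**Step 3. Does another section settle it?** The contents list runs Section 7 from 7.1 to 7.7.1 with no rescue section, and the body has none. Section 3.6 does not name hyperglycaemia. Section 5.3.1 does not say what the subject is discontinued from, although sections 3.6 and 3.7 treat stopping the drug and leaving the study separately.

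**Step 4. What section 8 does with each path**

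- Discontinued: the week 24 HbA1c and FPG are the last on-treatment values carried forward.
- Rescued and kept on study drug: the week 24 values are the observed ones, including the effect of the added drug.

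Section 8 flags adverse events that follow further therapy after study-drug discontinuation. That does not cover rescue while the subject is still on drug.

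**Step 5. Size per subject.** Inputs from the protocol: 200 subjects, 24 weeks of treatment.

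- Discontinuation percentage: 1/200 = 0.5 percentage points per subject.
- Exposure: at most 200 × 24/52 = 92.3 patient-years in total. A subject stopped at week w loses (24 − w)/52 years; at the week 8 visit that is 16/52 = 0.31 years, or 0.31/92.3 = 0.3% of the total.
- Mean HbA1c change: if the two paths give week 24 values differing by d percentage points, the mean over 200 subjects moves by d/200 per subject, which is 0.005 points for d = 1. The value d = 1 is a unit for scale, not an estimate.

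The number of subjects who would reach a confirmed glucose above 240 mg/dL is not in the protocol, so no total can be given.

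**The case against.** The strongest reply is that section 7.7, as shown, contradicts nothing. Its sentence stops before stating an action, and whether that is a drafting slip or a fault in the text as extracted cannot be told. The synopsis gives no glucose level. Both sides also leave room for judgement: 5.3.1 excuses explained hyperglycaemia, 7.7 lets the investigator decide who stays, and the general items in 3.6 on risk and on adverse events could cover a hyperglycaemic subject. One could even read the rules as a sequence, rescue first and discontinuation later.

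Much of this stands. The link from 7.7 to rescue is an inference, and so is any statement that a rescued subject remains on study drug. But no passage sets out a sequence. Even with 7.7 set aside, 5.3.1 directs discontinuation while the synopsis and the prohibited-therapies list permit rescue under criteria that cannot be found.

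A reader might also infer that the 9% figure clashes with eligibility, "HbA1c level >7.0% and ≤ 10% at screening visit", so that some subjects qualify for rescue before their first dose. The text does not support that. The 7.7 sentence speaks of glycaemia that stays uncontrolled, which implies persistence on treatment; it does not say whether HbA1c alone is enough; and an on-treatment threshold may lie inside the entry range. What remains is that no earliest time point is given. The protocol gives no HbA1c distribution, so a share of subjects in the 9% to 10% band cannot be derived from it.

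It is also true that the primary objective is descriptive safety, so the HbA1c and FPG effect touches secondary results only.

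**Conclusion.** The inconsistency is real and should be corrected. Discontinuation on confirmed fasting glucose above 240 mg/dL stands against permitted rescue during treatment, with a cited section that does not exist, an incomplete candidate criterion at essentially the same glucose level with a different confirmation rule, and no mention of hyperglycaemia in the discontinuation list.

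The effect on results is certain in kind and unknown in total: it depends on how many subjects reach the threshold and how sites divide. The conclusion assumes that rescue is meant to be possible while on study drug, which the exemption in the prohibited-therapies list implies but does not spell out. It does not rest on 7.7 being the rescue rule.

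**What to change.** - **Protocol.** The clinical team should reconcile the synopsis, section 3.6, section 5.3.1, section 7.7 and the prohibited-therapies list into one consistent passage. It should give the criterion, its confirmation, the earliest time point, the action, and whether discontinuation is from study drug or from the study. The 7.7 sentence should be completed and the synopsis cross-reference corrected. Which clinical rule is right is for the clinical team; none is proposed here.
- **Analysis.** Identify rescued subjects from the medication start dates and reasons that 7.7 already requires, and report week 24 HbA1c and FPG change with post-rescue values distinguished from the rest.

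The cost is one protocol clarification or amendment and a small addition to the efficacy tables. It needs no new eCRF field, no extra visits and no extra patients.
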